## 8. Discontinuation Criteria

### 8.1. Discontinuation from Study drug

#### 8.1.1. *Permanent Discontinuation from Study drug*

Possible reasons leading to permanent discontinuation of study drug:

- **Subject Decision**
  - the patient requests to discontinue study drug.
- **Discontinuation due to a hepatic event or liver test abnormality.**
  - Patients who are discontinued from study drug due to a hepatic event or liver test abnormality should have additional hepatic safety data collected via CRF.

Discontinuation of the study drug for abnormal liver tests should be considered by the investigator when a patient meets one of the following conditions after consultation with the Lilly designated medical monitor:

- ALT or AST >8x ULN
- ALT or AST >5xULN for more than 2 weeks
- ALT or AST >3xULN and total bilirubin level (TBL) >2xULN or international normalized ratio (INR) >1.5
- ALT or AST >3xULN with the appearance of fatigue, nausea, vomiting, right upper-quadrant pain or tenderness, fever, rash, and/or eosinophilia (>5%)
- ALP >3xULN
- ALP >2.5xULN and TBL >2xULN
- ALP >2.5xULN with the appearance of fatigue, nausea, vomiting, right quadrant pain or tenderness, fever, rash, and/or eosinophilia (>5%)

In addition, patients will be discontinued from the study drug in the following circumstances:

- Neutrophil (segmented) counts (see safety monitoring for neutropenia Section 9.4.6.1):
  - <500 cells/ $\mu$ L
  - $\geq$ 500 and <1000 cells/ $\mu$ L (based on 2 test results; the second test performed within 1 week from knowledge of the initial result)
  - $\geq$ 1000 and <1500 cells/ $\mu$ L (based on 3 test results as specified in Section 9.4.6.1) AND an infection that is not fully resolved
- Total WBC count <2000 cells/ $\mu$ L
- Lymphocyte count <200 cells/ $\mu$ L
- Platelet count <50,000 cells/ $\mu$ L
- The patient experiences a severe AE, an SAE, or a clinically significant change in a laboratory value occurs that in the opinion of the investigator, merits the discontinuation

of the study drug and appropriate measures being taken. In this case, Lilly or its designee is to be notified immediately via email and the event is to be documented.

- Clinically significant systemic hypersensitivity reaction following SC administration of study drug that does not respond to symptomatic medication or results in clinical sequelae
- The patient becomes pregnant

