- The patient develops a malignancy (Note: patients may be allowed to continue if they develop no more than 2 non-melanoma skin cancers during the study)
- if the patient develops active suicidal ideation with some intent to act with or without a specific plan (yes to question 4 or 5 on the “Suicidal Ideation” portion of the C-SSRS),

-OR-

if the patient develops suicide-related behaviors as recorded on the C-SSRS,

then it is recommended that the patient be assessed by a psychiatrist or appropriately trained professional to assist in deciding whether the patient is to be discontinued from the study.

Patients discontinuing from the study drug prematurely for any reason should complete AE and other follow-up procedures per Section 2 (Schedule of Activities), Section 9.2 (Adverse Events), and Section 9.4 (Safety) of this protocol.

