### 9.4.5. **Columbia-Suicide Severity Rating Scale**

The C-SSRS is a scale that captures the occurrence, severity, and frequency of suicidal ideation and/or behavior during the assessment period. The scale includes suggested questions to solicit the type of information needed to determine if suicidal ideation and/or behavior occurred. The C-SSRS is administered by an appropriately trained healthcare professional with at least 1 year of patient care/clinical experience or some or all of the patients may have this data solicited through electronic patient-reported outcomes (ePRO) technology. The tool was developed by the National Institute of Mental Health trial group (TASA) for the purpose of being a counterpart to the Columbia Classification Algorithm of Suicide Assessment categorization of suicidal events. Patients will be assessed according to the Schedule of Activities (Section 2). The Self-Harm Supplement Form is a 1-question form that asks for the number of suicidal or nonsuicidal self-injurious behaviors the patient has experienced since the last assessment. For each unique event identified, a questionnaire (Self-Harm Follow-Up Form) which collects supplemental information on the self-injurious behavior is to be completed. The Self-Harm Supplement Form will be completed according to the Schedule of Activities (Section 2).

The non-leading AE collection should occur prior to the collection of the C-SSRS. If a suicide-related event is discovered during the C-SSRS, but was not captured during the non-leading AE collection, sites should not change the AE form. If an event is serious or leads to discontinuation, this is an exception where the SAE and/or AE leading to discontinuation should be included on the AE form and the process for reporting SAEs should be followed.

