#### 10.3.4.3. Other Safety Evaluations

Suicide-related thoughts and behaviors and self-injurious behavior with no suicidal intent, based on the C-SSRS, will be listed by patient.

Further details for these analyses will be provided in the SAP.

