
Malignancies
	
Malignancy is defined using PTs from the Malignant or unspecified tumors SMQ as defined in MedDRA (SMQ: 20000091, which includes the sub-SMQs: (1) 20000194 [Malignant tumours], including sub-SMQs of 20000227 [Haematological malignant tumours] and 20000228 [Non-haematological malignant tumours]; (2) 20000195 [Tumours of unspecified malignancy], including sub-SMQs of 20000229 [Haematological tumours of unspecified malignancy] and 20000230 [Non-haematological tumours of unspecified malignancy].
 
Events will be summarized by the following categories:
 
 • Non-Melanoma Skin Cancer (NMSC) 
 ○ Basal Cell Carcinoma, PTs include: 
 ▪ Basal cell carcinoma ▪ Basosquamous carcinoma ▪ Basosquamous carcinoma of skin ○ Squamous Cell Carcinoma, PTs include: 
 ▪ Squamous cell carcinoma of skin ▪ Bowen’s disease ▪ Lip squamous cell carcinoma ▪ Skin squamous cell carcinoma metastatic ▪ Keratoacanthoma • Malignancies excluding NMSC: all PTs in the Malignant or unspecified tumors SMQ excluding the 8 defined NMSC PTs. 	
Blinded Treatment Periods (Fisher’s exact test): TEAE by PT within Category

Depressions	Depression is defined using the PTs from the Depression and suicide/self-injury SMQ as specified in MedDRA (SMQ: 20000035, which includes the sub-SMQs: 20000037 [Suicide/self-injury] and 20000167 [Depression (excl. suicide and self-injury)]).	Blinded Treatment Periods (Fisher’s exact test): TEAE by PT within SMQ or sub-SMQ
Interstitial Lung Disease (ILD)	ILD is defined using the PTs: 
 • Narrow terms in the Interstitial Lung Disease SMQ (20000042) • Additional 6 PTs from Eosinophilic Pneumonia SMQ (20000157): 
 ○ Angiolymphoid hyperplasia with eosinophilia (Narrow) ○ Eosinophilic bronchitis (Narrow) ○ Hypereosinophilic syndrome (Narrow) ○ Löeffler’s syndrome (Narrow) ○ Pulmonary eosinophilia (Narrow) ○ Pulmonary vasculitis (Narrow) 	

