6.14.4. Columbia-Suicide Severity Rating Scale (C-SSRS)

Given that few or no suicidal ideation or behaviors are anticipated, C-SSRS will be listed by patient and visit. Only patients that show suicidal ideation/behavior or self-injurious behavior without suicidal intent will be displayed (i.e., if a patient's answers are all "no" for the C-SSRS, then that patient will not be displayed). However, if a patient reported any suicidal ideation/behavior or self-injurious behavior without suicidal intent at any time point, then all his/her ideation and behavior will be displayed, even if not positive.

The Self-Harm data will be listed by patient and visit if number of events on Self-Harm Supplement Form is not zero in the *Self Harm Questionnaire Supplement* eCRF.

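### The SAP's between-arm suicidality comparison omits non-serious events found only on the C-SSRS unless they lead to discontinuation, and the C-SSRS itself is never compared by arm

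*Protocol*

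**What the plan says.** **AE capture.** Protocol 9.4.5 puts non-leading AE collection before the C-SSRS. If the C-SSRS then reveals a suicide-related event, "but was not captured during the non-leading AE collection, sites should not change the AE form". One carve-out follows: "If an event is serious or leads to discontinuation, this is an exception", and such events do go on the form.

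**The discontinuation decision.** Protocol 8.1.1 has a list introduced by "In addition, patients will be discontinued from the study drug in the following circumstances". One item in it begins "if the patient develops active suicidal ideation with some intent to act with or without a specific plan" (yes to ideation question 4 or 5) and has suicide-related behaviour on the C-SSRS as its alternative trigger. The action attached is not a stop: "then it is recommended that the patient be assessed by a psychiatrist or appropriately trained professional to assist in deciding whether the patient" is to leave the study. The lead-in concerns study drug; the item ends by referring to the study.

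**The comparison.** Depression is an adverse event of special interest (Protocol 9.2.1.2). SAP Table RHCR.6.8 states: "Depression is defined using the PTs from the Depression and suicide/self-injury SMQ". The analysis is treatment-emergent AEs by preferred term, compared between arms by Fisher's exact test over the Blinded Treatment Periods (SAP 6.14.3.1).

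**The C-SSRS.** SAP 6.14.4 says "C-SSRS will be listed by patient and visit". Protocol 10.3.4.3 agrees: suicidality findings, "based on the C-SSRS, will be listed by patient". Yet Protocol 10.3.4 and SAP 6.14 both name the C-SSRS among the safety data to be summarised and analysed.

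**The concern.** The trial asks every patient about suicidal ideation and behaviour with a structured scale at each treatment visit, then compares the arms on a different source that excludes part of what the scale finds. The excluded part is defined by something that happens after the event: whether the patient was discontinued because of it. Two patients with the same C-SSRS answers, neither event volunteered nor serious, are counted differently if one stops and the other continues.

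A reader of the depression table would not know this. An arm could show no events while the C-SSRS recorded some, and nothing else in the planned output gives a count or percentage by arm. For an event class that the sponsor has singled out, the compared count should not depend on a management decision.

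**Working it through.** The plan states no figure on this point, so there is none to reproduce. The check is mainly a reading of the text, followed by an illustration of size.

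**Step 1. Where each kind of event ends up** (Protocol 9.4.5; SAP 6.14.3.1, Table RHCR.6.8 and 6.14.4)

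| Suicide-related event on the C-SSRS | AE form | Depression table* | C-SSRS listing |
|---|---|---|---|
| Already captured by non-leading AE collection | Yes | Yes | Yes |
| Not captured, serious | Yes | Yes | Yes |
| Not captured, non-serious, leads to discontinuation | Yes | Yes | Yes |
| Not captured, non-serious, patient continues | No | No | Yes |

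*Provided that the event is treatment-emergent and codes to a term in the query.

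Only the last two rows differ by the discontinuation decision. The general AE tables in SAP 6.14.2 and 6.14.3 draw on the same AE form, so they do not fill the gap.

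**Step 2. Does the 8.1.1 wording cause this?** The item has its own operative clause, so the natural reading is to assess the patient and then decide. Under that single reading, each case can still fall in row 3 or row 4. The dependence comes from the 9.4.5 exception combined with an AE-only comparison. Rewording 8.1.1 while keeping a decision to continue or stop leaves it in place.

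**Step 3. How often the scale is asked.** Post-baseline treatment visits with a C-SSRS in the Schedule of Activities: Weeks 1, 2, 4, 6, 8, 10, 12 (7 visits) and Weeks 16, 20, 24 (3 visits); 7 + 3 = 10.

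**Step 4. Illustration of size.** Inputs: 480 per arm (planned, Protocol 10.1). Event counts are assumptions, taken from 0 to 6 per arm, because the documents give no rate and SAP 6.14.4 anticipates few or none.

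- If k patients in an arm have an event in rows 3 or 4, the table shows between 0 and k of them.
- For k = 3, if all stop: 3/480 = 0.625%, exact 95% CI 0.13% to 1.82%. If all continue: 0/480, upper limit 1 − 0.025^(1/480) = 0.77%.
- With all m events in one of two equal arms, two-sided Fisher p = 2 × C(480, m)/C(960, m):

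| Recorded events | p |
|---|---|
| 6 vs 0 | 0.031 |
| 5 vs 0 | 0.062 |
| 4 vs 0 | 0.124 |
| 3 vs 0 | 0.249 |
| 1 vs 0 | 1.0 |

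Six true events against none, with two patients continuing and so unrecorded, would appear as 4 vs 0: p moves from 0.031 to 0.124. With 0 or 1 event per arm, no test result changes.

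**Step 5. Efficacy.** One patient is 100/480 = 0.21 percentage points of an arm's response rate.

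**The case against.** The strongest reply is that this is a deliberate reporting design. Non-leading collection keeps the AE data free of prompting by the scale, serious events and those leading to discontinuation are added back, and the SAP gives its reason for a listing: few or no cases are expected. The listing shows all ideation and behaviour for any patient with a positive report, and non-zero self-harm data are listed too. The affected set is narrow. Entry excludes patients with a recent attempt, ideation with intent or judged suicide risk, and the important-medical-event criterion for seriousness may capture some of the remainder. The p-value changes above need counts that the SAP does not expect, and no decision rule depends on that p-value.

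Most of this stands. It justifies the non-leading rule and keeps the effect small. It does not explain why the scale's own data get no count by arm, when both documents name the C-SSRS among the data to be summarised and analysed.

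A reader might also infer something stronger: that the clash in 8.1.1 between a mandatory lead-in and a discretionary item makes the count depend on which reading a site adopts. The documents do not support that as the cause. Other items under the same lead-in carry their own discretion (investigator opinion on AEs and laboratory changes; tolerance of up to two non-melanoma skin cancers), the section opens by speaking of possible reasons, and the specific clause governs. As Step 2 shows, the count varies under that one reading.

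**Conclusion.** The point holds as a gap in safety reporting. The planned suicidality comparison is incomplete for non-serious events found only on the C-SSRS, and its completeness depends on case-by-case discontinuation decisions. The 8.1.1 wording is a separate, minor slip.

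The size is small. No direction of bias should be inferred: the assessing investigators and patients are blinded. Nor are cases lost, since each remains in the listing and serious events reach the AE form regardless. Efficacy conclusions do not depend on this. The numerical illustration rests on assumed counts and on 480 dosed patients per arm. If the SAP's expectation of few or no events proves right, the depression table may be unaffected. The change is still worth making because it costs almost nothing and gives a count that does not depend on whether the patient was discontinued.

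**What to change.** **SAP 6.14.4 (main change).** Add one table by arm for the Blinded Treatment Periods, safety population: number and percentage of patients with any post-baseline yes to C-SSRS ideation question 4 or 5, or any suicidal behaviour, whether or not the event is on the AE form. Use Fisher's exact test, which SAP 6.1.3 already assigns to categorical safety data. Keep the listing.

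**SAP Table RHCR.6.8.** Footnote the depression output: events detected only on the C-SSRS that were not serious and did not lead to discontinuation are not included.

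The 9.4.5 rule can stay. These two changes use data already collected, need no protocol amendment, and can be made before database lock.

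**Protocol 8.1.1 (minor wording).** Move the C-SSRS item out from under the mandatory lead-in and make the decision refer to study drug instead of the study. This can go into the next amendment or a clarification to sites. By itself it does not repair the count.

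**Optional safety addition.** Withhold the dose until the investigator has documented the decision. This changes conduct and should be weighed separately. With make-up windows of 3 days up to Week 12 and 5 days after it (Protocol 7.3.1), its cost is an occasional delayed or missed dose.

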### **8.1.2. Discontinuation of Inadvertently Enrolled Patients**

The criteria for enrollment must be followed explicitly.

If the sponsor or investigator identify a patient who did not meet enrollment criteria and was inadvertently enrolled, then the patient should be discontinued from study treatment unless there are extenuating circumstances that make it medically necessary for the patient to continue on study drug. If the investigator and the sponsor CRP agree it is medically appropriate to continue, the investigator must obtain documented approval from the sponsor CRP to allow the inadvertently enrolled patient to continue in the study with or without treatment with study drug. Safety follow-up is as outlined in Section 2 (Schedule of Activities), Section 9.2 (Adverse Events), and Section 9.4 (Safety) of the protocol.

## **8.2. Discontinuation from the Study**

Patients will be discontinued in the following circumstances:

- enrollment in any other clinical study involving an study drug or enrollment in any other type of medical research judged not to be scientifically or medically compatible with this study
- participation in the study needs to be stopped for medical, safety, regulatory, or other reasons consistent with applicable laws, regulations, and good clinical practice

- investigator decision
  - the investigator decides that the patient should be discontinued from the study
  - if the patient for any reason, requires treatment with another therapeutic agent that has been demonstrated to be effective for the treatment of the study indication, discontinuation from the study occurs before introduction of the new agent
- subject decision
  - the patient requests to be withdrawn from the study

Patients discontinuing from the study prematurely for any reason should complete AE and other safety follow-up per Section 2 (Schedule of Activities), Section 9.2 (Adverse Events), and Section 9.4 (Safety) of this protocol.

### **8.3. Lost to Follow-Up**

A patient will be considered lost to follow-up if he or she repeatedly fails to return for scheduled visits and is unable to be contacted by the study site. Site personnel are expected to make diligent attempts to contact patients or their families/relatives who fail to return for a scheduled visit or were otherwise unable to be followed up by the site.

Lilly personnel will not be involved in any attempts to collect vital status information.

## 9. Study Assessments and Procedures

Section 2 lists the Schedule of Activities, with the study procedures and their timing (including tolerance limits for timing). All study assessments except for the C-SSRS, Self-Harm, and Self-Harm Follow-Up will be completed electronically.

Appendix 2 lists the laboratory tests that will be performed for this study.

Unless otherwise stated in the subsections below, all samples collected for specified laboratory tests will be destroyed within 60 days of receipt of confirmed test results. Certain samples may be retained for a longer period, if necessary, to comply with applicable laws, regulations, or laboratory certification standards.

### 9.1. Efficacy Assessments

#### 9.1.1. Primary Efficacy Assessments

The primary efficacy endpoint is PASI 100 response at Week 12 (Visit 9).

##### 9.1.1.1. Psoriasis Area and Severity Index

The PASI is an accepted primary efficacy measurement for this phase of development of Ps treatments (EMA 2004). The PASI combines assessments of the extent of body-surface involvement in 4 anatomical regions (head, trunk, arms, and legs) and the severity of desquamation (scaling), erythema, and plaque induration/infiltration (thickness) in each region, yielding an overall score from 0 for no Ps up to 72 for the most severe disease (Fredriksson and Pettersson 1978). The PASI has been the most frequently used endpoint and measure of Ps severity in clinical trials (EMA 2004; Menter et al. 2008). A clinically meaningful response is a PASI 75, which represents at least a 75% decrease (improvement) from the baseline PASI score. Higher levels of clearance (PASI 90), as well as complete resolution of Ps (PASI 100), have become additional endpoints because of the increasing recognition of the association of higher clearance with greater health-related quality of life (Puig 2015).

#### 9.1.2. Major Secondary Efficacy Assessments

##### 9.1.2.1. Static Physician Global Assessment

The sPGA is the physician's determination of the patient's Ps lesions overall at a given time point. The sPGA is recommended as an endpoint to assess efficacy in the treatment of Ps (EMA 2004). Overall, lesions are categorized by descriptions for induration, erythema, and scaling. For the analysis of responses, the patient's Ps is assessed as clear (0), minimal (1), mild (2), moderate (3), severe (4), or very severe (5).

#### 9.1.3. Other Efficacy Assessments

##### 9.1.3.1. Percentage of Body Surface Area

The investigator will evaluate the percentage involvement of Ps on each patient's BSA on a continuous scale from 0% (no involvement) to 100% (full involvement), in which

1% corresponds to the size of the patient's hand (including the palm, fingers, and thumb) (Thomas and Finlay 2007).

### **9.1.3.2. Physician's Global Assessment of Disease Activity Visual Analog Scale (for Patients with PsA)**

The investigator will be asked to give an overall assessment of the severity of the patient's current PsA activity using a 100-mm horizontal visual analog scale (VAS), where 0 represents no disease activity and 100 represents extremely active disease. The investigator making the assessment must be a rheumatologist or medically qualified physician. The same assessor should preferably perform the Physician's Global Assessment of Disease Activity VAS for a given patient to minimize inter-observer variation.

### **9.1.3.3. PGA-F Physician's Global Assessment of Fingernail Psoriasis**

The Physician's Global Assessment of Fingernail Psoriasis (PGA-F), was developed for clinicians to evaluate the severity of fingernail abnormalities in patients with nail psoriasis. The scale assesses the nail bed and nail matrix signs of disease on a 0 to 4 scale (0 - clear, 1 - minimal, 2 - mild, 3 - moderate, 4 - severe).

## **9.1.4. Health Outcome Endpoints**

### **9.1.4.1. Itch Numeric Rating Scale**

The Itch NRS is a patient-administered single-item 11-point horizontal scale anchored at 0 and 10, with 0 representing "no itch" and 10 representing "worst itch imaginable." Patients indicate their overall severity of itching from Ps by circling the number that best describes the worst level of itching in the past 24 hours.

### **9.1.4.2. Skin Pain Visual Analog Scale**

The Skin Pain VAS is a patient-administered scale designed to measure skin pain from Ps using a 100-mm horizontal VAS. Overall severity of a patient's skin pain from Ps at the present time is indicated by placing a single mark on the horizontal scale (0 = no skin pain; 100 = severe skin pain).

### **9.1.4.3. Patient's Global Assessment of Disease Severity**

The Patient's Global Assessment of Disease Severity is a patient-administered, single-item scale on which patients are asked to rank, by circling a number on a 0 to 5 NRS, the severity of their Ps "today" from 0 (clear), no Ps; to 5 (severe).

